- ^l The Study Termination Visit includes the study drug termination which should be pconducted at the time the decision is made to discontinue the study drug (prior to down titration), either because the subject has met clinical worsening criteria or is being permanently discontinued from the 310 study. The 6MWD should be conducted within 3 to 6 hours after the most recent dose of study medication and preferably before the drug is down titrated (if the subject is being permanently discontinued rather than transitioning to the TDE-PH-311 study)
- ^m If subject permanently discontinues study drug before Week 24 and is ineligible for the TDE-PH-311 study, subject should be encouraged to remain in study and attend visits up to and including Week 24. The end of study assessments (survival status, AE assessment, drug accountability, concomitant medications, etc.) should be conducted after the subject has stopped taking the study medication (before or at Week 24)
- ⁿ Weekly telephone contact should be completed and subject study drug dose must also be recorded at Week 16 and Week 20 in the eCRF. More frequent telephone calls may be necessary depending on the frequency of dose titration and to manage AEs or signs and symptoms of disease
- ^o For subjects consenting to the optional biomarker samples.
- ^p For subjects consenting to the optional pharmacogenomic sample.

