Prior to Week 24, if the Investigator, for any reason, initiates a second PAH-approved oral therapy in addition to the PAH-approved oral therapy initiated prior to Screening (e.g., due to disease progression without meeting the definition of clinical worsening as defined in [Section 2.1](#)), the subject must be discontinued from the study drug. The subject should be encouraged to remain in the study and attend all visits up to and including Week 24; however, the subject will not be eligible for enrollment in the open-label study (TDE-PH-311). After Week 24, if the Investigator initiates a second PAH-approved oral therapy due to any reason in addition to the PAH-approved oral therapy initiated prior to Screening, the subject must be discontinued from the study and will not be eligible for enrollment in the open-label study.

All changes in drug or dosage regimens during the study will be recorded in the subject's source documents and transcribed as required to the eCRF.

Product labeling for the background PAH-approved oral therapy should be consulted in order to guide the monitoring of AEs. The dose of study drug should be adjusted first in response to any new AEs that occur during the study, rather than adjusting the dose of PAH-approved oral therapy; unless the event is considered causally related to the PAH-approved oral therapy. If a subject meets the definition of clinical worsening during the study and receives only short term (28 days or less) treatment with an infused or inhaled PGI₂ therapy for worsening PAH, they will be permitted to enter the open-label extension study (TDE-PH-311). If a subject prematurely discontinues the study for any reason other than clinical worsening, or receives long-term (29 days or more) treatment with an infused or inhaled PGI₂ therapy for worsening PAH, they will not be permitted to enter the open-label extension study. During the course of the study, if the Investigator initiates a second PAH-approved oral therapy due to any reason (e.g. disease progression without meeting the definition of clinical worsening as defined in Section 2.1) in addition to the PAH-approved oral therapy initiated prior to Screening, the subject must be discontinued from the study and will not be eligible for enrollment in the open-label study (TDE-PH-311).

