7.4 STUDY DRUG TERMINATION VISIT

Subjects will continue in the study until they experience clinical worsening, prematurely discontinue the study for any reason, or approximately 205 adjudicated clinical worsening events have occurred. If a subject remains ongoing with study treatment at the time when approximately 205 adjudicated clinical worsening events have occurred, the Study Drug Termination Visit should be scheduled as soon as possible. The following assessments will be conducted immediately after the decision is made to discontinue study drug (prior to down titration).

- Vital signs (following at least 5 minutes of rest)
- Physical examination
- Clinical worsening assessment
- WHO Functional Class for PAH
- AE assessment
- Drug accountability/compliance
- 12-lead ECG (following at least 5 minutes rest in the semi-recumbent position)
- Concomitant medications
- 6MWT/Borg dyspnea score (6MWT to be initiated 3 to 6 hours after last dose of study drug and following at least 5 minutes of rest; Borg dyspnea score to be conducted immediately following 6MWT)
- Urine pregnancy test (for WOCBP)
- Clinical laboratory tests/NT-proBNP

- Collection of blood sample for evaluation of blood biomarkers (optional)
- Collection of urine sample for evaluation of urine biomarkers (optional)
- Collection of blood sample for evaluation of pharmacogenomics (optional)

If the subject permanently discontinues study drug prior to Week 24 for any reason other than clinical worsening (e.g., AEs, addition of second PAH-approved oral therapy), the subject should immediately complete the study drug termination visit assessments and be encouraged to remain in the study and complete all visits up to and including Week 24. The Study Drug Termination Visit assessments should be conducted immediately after the decision is made to discontinue study drug (prior to down titration).

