9.2 DOCUMENTATION OF ADVERSE EVENTS

AEs will be captured from the time the ICF is signed. An AE or SAE occurring during the study, following completion of the ICF, must be documented in the subject's source documents and on the appropriate eCRF page. Information relating to the AE such as onset and cessation date and times, intensity, seriousness, relationship to study drug, and outcome is also to be documented in the eCRF (see Section 15.4 for definitions). Where possible, AEs should be recorded using standard medical terminology. If several signs or symptoms are clearly related to a medically defined diagnosis or syndrome, the diagnosis or syndrome should be recorded on the eCRF page, not the individual signs and symptoms.

All AEs should be followed until either resolution (or return to normal or pre-randomization values), until they are judged by the Investigator to no longer be clinically significant, or for up to 30 days if the AE extends beyond the final visit. All SAEs that occur during the study will be followed until resolution, death, or the subject is lost to follow-up even if they are ongoing more than 30 days after completion of the final visit. Supplemental measurements and/or evaluations may be necessary to investigate fully the nature and/or causality of an AE or SAE. This may include additional laboratory tests, diagnostic procedures, or consultation with other healthcare professionals. The eCRF pages should be updated with any new or additional information as appropriate.

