### 12.2 ADVERSE EVENTS

All AEs will be coded using MedDRA and will be listed by treatment group, including all the details on the eCRF page plus an indicator of whether the event was treatment emergent. The AE listings will include the AE verbatim term and its corresponding PT and SOC.

The AE summary tables will be limited to include only treatment-emergent AEs and will be summarized for each treatment group. Treatment-emergent AEs are those AEs with an onset date equal to or after the start date of the study drug. The non-treatment emergent AEs (the AEs that occur after signing the informed consent form, but before receiving study drug, will be listed but will not be included in summary tables.

All summaries will include the number and percentage of subjects experiencing each type of event based on PT and the total number of each type of event, in order of overall frequency and/or SOC. Serious AEs and non-serious AEs will be summarized by PT.

Maximum level of seriousness and intensity occurring during the treatment phase for each AE will be summarized separately and by causality (probable or possible versus not related).

Considering the potential imbalance in treatment exposure, the total number of AEs and the AE rate will be calculated and summarized. The AE rate will be calculated as the total number of AEs divided by the total patient years per treatment group.

Separate listings and summary tables will be provided for all serious adverse events (SAEs), AEs leading to the discontinuation of the study drug, and all deaths during the study.

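### The treatment-emergent AE window in SAP 12.2 has a start but no end, so off-drug AEs enter the main tables and an AE rate whose patient-years are undefined; the effect is modest and the fix cheap.

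*SAP*

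**What the plan says.** SAP 12.2 restricts the AE summary tables to treatment-emergent events: "Treatment-emergent AEs are those AEs with an onset date equal to or after the start date of the study drug". The only AEs it removes are those arising ahead of the first dose: "the AEs that occur after signing the informed consent form, but before receiving study drug, will be listed but will not be included in summary". Because exposure may differ between arms, it adds a rate: "The AE rate will be calculated as the total number of AEs divided by the total patient years per treatment group". SAP 6 groups safety data by treatment actually received.

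Protocol 9.2 collects AEs whether or not the subject is on drug: "An AE or SAE occurring during the study, following completion of the ICF, must be documented". Its 30-day wording, "for up to 30 days if the AE extends beyond the final visit", concerns how long an ongoing AE is followed.

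Protocol 7.4 says that a subject who permanently stops study drug before Week 24 for a reason other than clinical worsening should "be encouraged to remain in the study and complete all visits up to and including Week 24". Its examples of such reasons are AEs and the addition of a second oral PAH therapy. Protocol 4.3.1 repeats this for a second oral therapy started before Week 24: "The subject should be encouraged to remain in the study and attend all visits up to and including Week 24". Protocol 7.3 lists an AE assessment at Weeks 4, 8, 12 and 24.

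**The concern.** The protocol deliberately follows some subjects off drug, and the SAP has no rule separating AEs that arise then from those on drug. The main AE tables would mix the two, including AEs that start after a new oral PAH therapy.

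The rate inherits the problem. If patient-years means exposure, the numerator includes events from time missing in the denominator, and the rate is too high. If it means follow-up, the rate averages on-drug and off-drug periods and can pull a real drug effect towards the null. Two programmers could report different rates from the same data.

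More early stopping on UT-15C is plausible, so the distortion need not cancel between arms.

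**Working it through.** **Does any other text close the window?** The 30-day phrase in Protocol 9.2 limits follow-up of an ongoing AE, not onset. SAP 12.2 summarises maximum intensity and seriousness during the treatment phase, but does not define that phase. Elsewhere the SAP does deal with off-drug data. SAP 10.1.1.2 drops non-fatal worsening more than 7 days after permanent discontinuation and counts deaths to 30 days after the last dose. SAP 10.2.1 excludes walk distances after drug termination from its non-parametric analysis, and SAP 10.2.1.1 restores them as a sensitivity analysis. AEs have no equivalent rule.

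**How long can off-drug collection last?** A stop at Week 4 leaves 24 − 4 = 20 weeks. The extreme is a stop just after Day 1 with the Week 24 visit (Day 169) at +7 days: (169 + 7 − 1)/7 = 25 weeks. The long window mainly concerns stops before Week 24. A second oral therapy started later takes the subject out of the study (Protocol 4.3.1).

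**How much person-time?** The plan states no figure to reproduce, so this is an illustration.

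From the documents:
- 610/2 = 305 per arm (Protocol 10.2)
- 22% vs 14% discontinuing, from the earlier 16-week BID study TDE-PH-301 (Protocol 1.2.4)
- medians of 51 and 32 months, accrual over 3 years (Protocol 10.2), duration 4 years (Protocol 3.5)

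Assumed: mean stop at Week 8, 50–100% of stoppers retained to Week 24, uniform accrual, no later dropout, and the same AE rate off drug as on drug within each arm.

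| Step | UT-15C | Placebo |
|---|---|---|
| Stoppers | 0.22 × 305 = 67 | 0.14 × 305 = 43 |
| Off-drug years, all retained | 67 × 16/52.18 = 20.5 | 43 × 16/52.18 = 13.2 |
| Off-drug years, half retained | 10.3 | 6.6 |
| On-drug years, first 24 weeks | (238×24 + 67×8)/52.18 = 119.7 | (262×24 + 43×8)/52.18 = 127.1 |
| Inflation, first 24 weeks (off/on) | 8.6–17.2% | 5.2–10.4% |

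The AE tables cover the whole study, so the whole-study denominator matters more. With λ = ln 2/median and follow-up uniform on 12–48 months, mean time on drug for those who do not stop early is (1/λ)[1 − (e^(−12λ) − e^(−48λ))/(36λ)].

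- UT-15C: λ = 0.01359 per month, mean 24.15 months. On-drug years: 238 × 24.15/12 + 67 × 8/52.18 = 478.9 + 10.3 = 489. Inflation: 10.3/489 = 2.1% to 20.5/489 = 4.2%.
- Placebo: λ = 0.02166 per month, mean 21.45 months. On-drug years: 262 × 21.45/12 + 43 × 8/52.18 = 468.2 + 6.6 = 475. Inflation: 6.6/475 = 1.4% to 13.2/475 = 2.8%.
- Between-arm rate ratio: multiplied by 1.021/1.014 = 1.007 to 1.042/1.028 = 1.014.

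**If the denominator is follow-up.** Suppose the true on-drug ratio is 1.50 and the off-drug rate in both arms equals the placebo rate. The whole-study ratio becomes (1.5 × 489 + 20.5)/(489 + 20.5) = 1.48 with full retention, or (1.5 × 489 + 10.3)/(489 + 10.3) = 1.49 with half. For the first 24 weeks alone, a wider set of assumptions (mean stop at Week 4–12, 25–100% retained, off-drug rate 0.5–2 times placebo) turns a true 1.50 into 1.40–1.49 with follow-up years and 1.50–1.54 with exposure years.

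**The case against.** The inputs are soft. TDE-PH-301 dosed BID and began with a 1 mg starting dose. Its subjects with 0.25 mg tablets at randomisation had no AE discontinuations (n = 23), and this trial starts at 0.125 mg. The 22% and 14% are all-cause and may include deaths and worsening, which do not lead to retention under Protocol 7.4. Staying is only encouraged. The SAP also offers partial handling: AEs by causality, and Table 14.3.1.13 by study drug dose at onset. Listed PAH-progression events that the investigator attributes to progression are not recorded as AEs unless serious, possibly drug-caused or worse than expected (Protocol 9.1.3).

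All this stands as a reason to call the size modest. It does not supply an end to the window, and the SAP gives no rule for placing an off-drug AE in a table by dose at onset.

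A reader might infer three stronger things.

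- *Rescue PGI₂ AEs on placebo will pile up off drug.* The text does not settle this. Starting PGI₂ for worsening PAH is itself a worsening event leading to the termination visit (Protocol 3.2.1.1), and Protocol 7.4 retains only those who stop for other reasons. Table 3-1 footnote m is wider: for anyone stopping before Week 24 and ineligible for TDE-PH-311, "subject should be encouraged to remain in study and attend visits up to and including Week 24". That could include long-term PGI₂ users. Nor would an end date remove AEs from PGI₂ given while the subject is still on study drug.
- *The AEs are charged to the randomised drug.* Safety groups follow treatment received.
- *Rates are inflated by 9–17%.* That holds only against first-24-week exposure, not the whole study.

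**Conclusion.** The point holds as a minor-to-moderate defect of definition. Followed as written, SAP 12.2 places off-drug AEs, including those arising on a second oral therapy started before Week 24, in the main tables and in the rate. On the assumptions above, an exposure-based rate over the whole study rises by about 2–4% on UT-15C and 1–3% on placebo, and the between-arm ratio by about 1%. A follow-up denominator would shrink a true ratio of 1.50 to about 1.48–1.49. Early AE displays, if produced, would be affected more. Only the 22% and 14%, the sample size, the medians and the accrual and study durations come from the documents; stop time, retention and off-drug AE rate are assumed. No efficacy result or sample-size figure is affected.

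**What to change.** In SAP 12.2:

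1. End the treatment-emergent window a fixed time after the last study-drug dose, or at entry to TDE-PH-311 if earlier. Thirty days would match the follow-up period that SAP 10.1.1.2 and 12.3 use for deaths; the length is the sponsor's choice.
2. Tabulate later AEs separately as post-treatment.
3. Flag AEs with onset after a second oral PAH therapy or PGI₂ was started. The flag is needed because PGI₂ may begin inside the window.
4. Define patient-years as the person-time over which the numerator is counted.

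Two protocol inconsistencies should be reconciled because they decide who contributes off-drug AEs. Table 3-1 footnote m and section 7.4 differ on who is retained to Week 24. Within section 4.3.1, one paragraph keeps subjects on a second oral therapy in the study before Week 24, while the closing sentence discontinues them at any time.

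The cost is a few sentences of SAP text, two derived flags and one extra table. Late AEs move from the main table to the second, and none is lost.

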The primary efficacy analysis comparing change in 6MWD from Baseline to Week 12 between treatment groups in the primary analysis population (n=228) was +23 m (p=0.0125, H-L estimate). The UT-15C group improved by a median of +25 m compared to -5 m change in the placebo group.

The combined 6MWD and Borg dyspnea score was also significantly improved ($p=0.0497$) at Week 12. Preliminary analysis of other secondary efficacy measures, including change in trough 6MWD at Week 11, change in dyspnea fatigue index, change in Borg dyspnea score, change in WHO Functional Class, time to clinical worsening (as defined by death, transplantation, atrial septostomy, hospitalization due to PAH or at least a 20% decrease in 6MWD and initiation of another approved PAH therapy), and PAH signs and symptoms at Week 12 did not differ significantly between the UT-15C and placebo groups ($p>0.05$).

An analysis of all 349 subjects enrolled in the study demonstrated that those subjects receiving UT-15C improved their median 6MWD by approximately +25.5 m (H-L estimate, $p=0.0001$) as compared to subjects receiving placebo.

AEs during the study included headache, nausea, diarrhea, and flushing, which were expected in subjects receiving prostanoid therapy. A low discontinuation rate due to AEs in the primary analysis population and the type of AEs resulting in discontinuation (mostly PGI₂ related, which are not life threatening) indicate that use of UT-15C may provide a significant improvement in the safety profile of treprostinil and result in a reduction in the occurrence of life-threatening AEs compared with parenteral treprostinil therapy (e.g., central venous catheter-related blood stream infection).

TDE-PH-308 was a 16-week, randomized, double-blind, placebo-controlled, international Phase 3 efficacy and safety study of UT-15C in patients with PAH. Patients received UT-15C or placebo BID in combination with either an ERA, a PDE5-I, or both. The primary endpoint was placebo-corrected change in 6MWD from Baseline to Week 16. Secondary endpoints included Borg dyspnea score, dyspnea-fatigue index, WHO Functional Class and time to clinical worsening. Study drug dose was titrated up to a maximum of 16 mg BID based on clinical response and study drug tolerability.

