9 ADVERSE EVENT REPORTING

9.1 DEFINITIONS

9.1.1 Adverse Event

An AE is any untoward medical experience occurring to a subject during a clinical trial whether or not it is related to the study drug. An AE may include an intercurrent illness, injury, or any other concomitant impairment of the subject's health, as well as abnormal laboratory findings if deemed to have clinical significance. AEs may also include worsening of an existing symptom or condition or pre/post-treatment events that occur as a result of protocol-mandated procedures.

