9.1.3 Adverse Events Associated with Progression of PAH

Expected events that are related to the progression of a subject's PAH are defined in Appendix 15.6. All events that occur during the course of the study that are included on this list and felt to be related to the progression of the disease by the Investigator should not be recorded as AEs in the eCRF as these PAH symptoms will be evaluated and recorded as an efficacy endpoint and/or will be captured as disease related events.

However, an event must be recorded as an AE/SAE in the eCRF, if it meets one or more of the following criteria:

- There is a reasonable possibility that it may have been caused by study drug.
- It is serious.
- It has occurred at greater than expected severity (intensity, frequency, or duration).

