15.4 GUIDELINES AND DEFINITIONS FOR RECORDING ADVERSE EVENTS

The Principal Investigator or a designated member of his/her staff will probe each subject for any AEs that may have occurred. The Investigator should always ask the same question when conducting the verbal probe in order to ensure uniformity between subjects. The Investigator should ask:

“How are you doing (feeling)?”

Based on the subject’s response to this question, the Investigator should ask additional questions relevant to the specific complaint such as:

“How severe is/was the symptom?”

“How often did the symptom occur?”

“How long did the symptom last?”

Using provided definitions, the Investigator will then:

(1) rate the intensity and seriousness of the AE, (2) estimate the causality of the AE to study drug, and (3) note actions taken to counteract the AE.

Definitions of Intensity, Seriousness, Causality, Action Taken, and Outcome

INTENSITY

An assessment of the relative intensity (severity) of an AE is based on the Investigator’s clinical judgment. The maximum intensity encountered during the evaluation period should be checked. The assessment of intensity should be independent of the assessment of the seriousness of the AE.

SERIOUSNESS

A serious AE is one that represents an actual or potential significant hazard. This includes, but is not limited to, an event that is fatal, life-threatening, permanently or severely disabling, requires or prolongs inpatient hospitalization, is a congenital abnormality (offspring of subject) or is medically significant (important medical events that may not result in death, be life-threatening, or require hospitalization may be considered a serious AE when, based upon appropriate medical

judgment, they may jeopardize the subject and may require medical or surgical intervention to prevent one of the outcomes listed in this definition).

CAUSALITY

An estimate of causality between a specified AE and the study drug is made by the Investigator. Definitions of the categories follow:

- NOT RELATED - there is not a temporal relationship to study drug administration (too early, or late, or study drug not taken), or there is a reasonable causal relationship between another drug, or concurrent disease and the SAE
- POSSIBLE - there is a reasonable causal relationship between the study drug and the SAE. Dechallenge information is lacking or unclear

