14.2.2.7	Summary and Analysis of 6MWD (meter) at Week 24 with No Imputation for Missing Data
14.2.2.8	Summary and Analysis of 6MWD (meter) at Week 24 Including Data Collected After Termination of Study Drug
14.2.2.9	Summary and Analysis of 6MWD (meter) at Week 24 by Etiology
14.2.2.10	Summary and Analysis of 6MWD (meter) at Week 24 by Baseline WHO Functional Class
14.2.2.11	Summary and Analysis of 6MWD (meter) at Week 24 by Geographic Region
14.2.2.12	Summary and Analysis of 6MWD (meter) at Week 24 by Sex
14.2.2.13	Summary and Analysis of 6MWD (meter) at Week 24 by Age Group
14.2.2.14	Summary and Analysis of 6MWD (meter) at Week 24 by Study Drug Dose
14.2.2.15	Summary and Analysis of 6MWD (meter) at Week 24 by UT-15C Dose Quartile at Week 24
14.2.2.16	Summary and Analysis of 6MWD (meter) at Week 24 by Background PAH Therapy
14.2.2.17	Summary and Analysis of 6MWD (meter) at Week 24 by Baseline 6MWD Category
14.2.2.18	Summary and Analysis of 6MWD (meter) at Weeks 4, 8, 12, 36, and 48
14.2.2.19	Summary of 6MWD (meter) by Visit with Observed Case
14.2.3.1	Summary and Analysis of NT-proBNP (pg/mL) Data at Week 24
14.2.3.2	Summary and Analysis of NT-proBNP (pg/mL) Data at Weeks 12 and 36

Table Number	Table Title
14.2.3.3	Summary and Analysis of NT-proBNP (pg/mL) Data at Weeks 12, 24, and 36 with LOCF Imputation
14.2.3.4	Summary of NT-proBNP (pg/mL) Data by Visit
14.2.3.5	Analysis of NT-proBNP (pg/mL) at Week 24 Using Mixed Model Repeated Measurement (MMRM) – ITT Population
14.2.3.6	Analysis of NT-proBNP (pg/mL) at Week 36 Using Mixed Model Repeated Measurement (MMRM) – ITT Population
14.2.4.1	Summary and Analysis of Borg Dyspnea Score up to Week 48
14.2.4.2	Summary of Borg Dyspnea Score by Visit with Observed Case
14.2.5.1	Summary and Analysis of WHO Functional Class up to Week 48
14.2.5.2	Summary of WHO Functional Class by Visit with Observed Case
14.2.6	Summary and Analysis of Hemodynamic Parameters at Week 24
14.2.7	Summary of Hospitalization Information
14.3.1.1	Overall Summary of Adverse Events
14.3.1.2	Summary of Adverse Events by System Organ Class and Preferred Term
14.3.1.3	Summary of Adverse Events by System Organ Class
14.3.1.4	Summary of Adverse Events by Preferred Term
14.3.1.5	Summary of Deaths
14.3.1.6	Summary of Serious Adverse Events by Preferred Term
14.3.1.7	Summary of Adverse Events Probably or Possibly Related to Study Drug by Preferred Term

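### SAP 12.2 defines treatment-emergent AEs by onset date alone, so a Screening-onset AE kept as one record that worsens on study drug is left out of the general AE tables

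*SAP*

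**What the plan says.** SAP 12.2 limits the AE summary tables to treatment-emergent events and gives one criterion for them: "Treatment-emergent AEs are those AEs with an onset date equal to or after the start date of the study drug". AEs that occur after consent but before study drug "will be listed but will not be included in summary tables". The AE listings carry an indicator of treatment emergence.

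On recording, Protocol 9.2 has AEs captured from signature of the consent form and eCRF pages updated as new information arrives. Protocol 9.1.1 says that "AEs may also include worsening of an existing symptom or condition". Protocol 15.4 asks for one maximum intensity per AE and only the last action taken with study drug.

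On causality, Protocol 15.4 rates an AE as not related where "there is not a temporal relationship to study drug administration (too early, or late, or study drug not taken". The SAP's list of tables (Section 16.1) includes Table 14.3.1.7, "Summary of Adverse Events Probably or Possibly Related to Study Drug by Preferred Term".

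**The concern.** A definition of treatment emergence usually has two parts: events that start on treatment, and events already present that get worse on it. SAP 12.2 has only the first.

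Suppose a subject has a mild headache during Screening that becomes severe during up-titration. If the site keeps one record, its onset date is before the first dose and the whole record leaves the summary tables. If another site enters the worsening as a new AE, the same clinical course is counted. The count then depends on recording habit.

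If on-drug worsening is more common on UT-15C than on placebo, the comparison of AE frequencies moves slightly towards no difference. An AE that the investigator judged drug-related could also be absent from the table meant to show such AEs.

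**Working it through.** The plan gives no figure on this point, so there is none to reproduce. The check is mainly textual.

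1. **Can pre-dose AE records exist?** Yes. Collection starts at consent (Protocol 9.2), and Screening can last up to 30 days (Protocol 7.1). Background PAH therapy may be titrated during Screening (Protocol 3.1), which is one plausible source of AEs still ongoing at first dose. Where Screening and Baseline are combined, the window is at most 48 hours.

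2. **Does either document require a new record on worsening?** No. Protocol 9.1.1 brings worsening within the meaning of an AE but does not tell sites to close one record and open another. Updating pages (9.2) and recording a single maximum intensity (15.4) are both consistent with one record that spans the first dose. They do not require it. The single record is an inference, not a stated rule.

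3. **Apply the SAP rule to a single record.** Onset is before first dose, so the AE is not treatment-emergent whatever its later intensity. It is left out of the overall table (14.3.1.1), the system organ class and preferred term tables (14.3.1.2 to 14.3.1.4), the related table (14.3.1.7), the non-serious table (14.3.1.9) and the seriousness, intensity and causality tables (14.3.1.10 to 14.3.1.12). SAP 12.2 speaks of maximum seriousness and intensity during the treatment phase, but this does not rescue the record, because those summaries are limited to treatment-emergent AEs as well.

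4. **Table 14.3.1.7.** Under Protocol 15.4 an event that is too early for study drug is not related. A pre-dose-onset record that is nevertheless rated possible or probable can only reflect what happened on drug. The onset rule still excludes it.

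5. **Which terms are exposed?** For PAH-progression events listed in Protocol 15.6 and attributed to progression, Protocol 9.1.3 says they "should not be recorded as AEs in the eCRF as these PAH symptoms will be evaluated and recorded as an efficacy endpoint", unless serious, possibly drug-caused or more severe than expected. On-drug worsening of these would usually be recorded for the first time after dosing, and so counted. For one earlier trial, Protocol 1.2.4 reports: "AEs during the study included headache, nausea, diarrhea, and flushing, which were expected in subjects receiving prostanoid therapy". Of those four terms only nausea is on the 15.6 list, so three of the four fall outside that exemption.

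6. **Illustrative size.** Every share below is an assumption; the documents supply none. For one preferred term:

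   lost risk difference = a × b × c × (p_UT-15C − p_placebo)

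   - a = share with a recordable AE of that term ongoing at first dose after a full Screening window: 0.5% to 2%
   - b = share with a separate Screening visit (combined visits counted as zero): 50% to 100%
   - c = share of worsenings kept as one record: 25% to 75%
   - p = probability of worsening: 30% to 50% on UT-15C, 10% on placebo

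   Arm sizes from Protocol 3.4: 610/2 = 305 and 850/2 = 425.

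   - Low: 0.005 × 0.50 × 0.25 × (0.30 − 0.10) = 0.000125, or 0.0125 percentage points; × 305 = 0.04 subjects
   - High: 0.02 × 1.00 × 0.75 × (0.50 − 0.10) = 0.006, or 0.6 percentage points; × 425 = 2.55, about 2.6 subjects

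   A later separate episode of the same term would be counted anyway, so the loss under these assumptions would be lower still.

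**The case against.** The best reply is that Protocol 9.1.1 already deals with this. There, the word may lists what falls within the definition of an AE; it does not make recording optional. Worsening of an existing condition is then an AE with its own onset, the date of worsening, and SAP 12.2 counts it. How sites split or extend records is normally settled in eCRF completion instructions, which are not among these documents. Protocol 15.4 points the same way: an investigator who blames study drug for the worsening cannot easily rate a pre-dose record as related, and would more naturally open a new one.

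The pool of events is also narrow. Prostanoid effects mostly begin on drug. Side effects of background therapy, which must have started at least 30 days before randomization, would mostly predate consent and be medical history. In a study estimated to last four years (Protocol 3.5), common events will often recur on drug.

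Much of this stands, and it narrows the point. It does not remove it, because no passage requires the new record and two recording rules fit a single one equally well.

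Two stronger readings are not supported. A reader might infer that sites must keep one record; the documents do not say so. A reader might also infer that serious AEs and AEs leading to discontinuation are lost from their own tables. SAP 12.2 says "Separate listings and summary tables will be provided for all serious adverse events (SAEs), AEs leading to the discontinuation of the study drug", with deaths also covered, and does not say whether the treatment-emergent limit applies. That leaves the question open and shows no loss.

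**Conclusion.** The point holds as a gap in a stated rule. A Screening-onset AE kept as one record and worsening on study drug is left out of the general AE tables, including 14.3.1.7. It depends on a recording practice that the documents neither require nor rule out.

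The effect is probably very small and cannot be estimated from the documents. The range of about 0.01 to 0.6 percentage points per term rests wholly on assumed shares and shows only the order of size. A reader might infer that the safety profile of UT-15C is materially understated. The documents do not support that: the window is short, a worsening entered as a new AE is counted, and every event stays in the listings. No efficacy analysis is affected. This is a minor improvement to the plan.

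**What to change.** - **Definition.** In SAP 12.2, add after the onset criterion: *or an AE with onset before first dose that worsens in intensity or becomes serious on or after first dose*.
- **Data entry still open.** Tell sites to record post-dose worsening of a Screening AE as a new AE dated at the worsening.
- **Single records already entered.** These hold a maximum intensity but no date of worsening, so the new clause cannot be fully derived from them. As a proxy, flag as treatment-emergent those with pre-dose onset that are rated possibly or probably related, or that have study drug recorded as reduced, interrupted or withdrawn. The proxy is incomplete, because only the last drug action is kept. It is conservative, because some flagged events may not have worsened. It applies in the same way to both arms.

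No change is proposed to Tables 14.3.1.6 (serious AEs) or 14.3.1.8 (AEs leading to discontinuation), for which no loss is claimed. None is proposed to Table 14.3.1.13 (dose at onset) either, since the dose at worsening would usually be unknown for a single record.

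The cost is one clause in the SAP, a short rule for the proxy with one derivation flag, and one line of eCRF guidance where entry is open. No protocol amendment is needed. The downside is slightly higher AE counts in both arms.
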